Currently available treatment options for these genitourinary symptoms of menopause (GSM) include use of lubricants with sexual intercourse, vaginal moisturizer a few times a week, twice weekly vaginal estrogen, a daily oral selective estrogen receptor modulator, or most recently vaginal dihydroepiandrosterone sulfate (DHEAS). All of these options require regular use of a medication, as a result several studies show high discontinuation rates of topical products⁷.

More recently, fractional carbon dioxide (fCO₂) laser treatment of the vaginal tissue has been proposed as a treatment for genitourinary symptoms of menopause. Laser treatment is a longstanding option for skin discoloration and scarring, and has been shown to induce collagen production and tissue remodeling⁸. Use of laser in gynecology presumes that vulvovaginal symptoms are due to the thinning of the vaginal mucosa and loss of underlying collagen that occurs with menopause. Examination of pre- and post-treatment vaginal biopsies shows a significant increase in vaginal mucosal thickness without damage to surrounding tissue^{9, 10}. Vaginal samples show an increase in lactobacillus colonization and decrease in pH¹¹. Case report and case series data suggest that the treatment is well tolerated by patients and is not associated with serious adverse events¹². Additionally, several case series demonstrate improvements in vulvovaginal^{13, 14} and urinary symptoms¹⁵, and in sexual function¹⁶.

However, these studies are from a select few centers, are small, and are also biased in that the laser treatment is only available to patients who are able to pay for it, although patients have reported that they found the cost worthwhile¹⁷. In addition, most studies report only on vulvovaginal symptoms, despite increasing use of laser for urinary symptoms. Several recent editorials have called for larger studies with longer follow-up and high quality outcome measures¹⁸⁻²⁰.

At Beaumont's Women's Urology and Pelvic Health Center, we have the unique opportunity to provide fractionated carbon dioxide laser vulvovaginal treatment for a wide range patients with vulvovaginal, sexual and urologic complaints.

Objectives and Outcomes

This study will evaluate the effect of fractional carbon dioxide laser therapy of the vagina in female patients with urogenital symptoms.

Urogenital symptoms may include vaginal itching, burning, dryness, dyspareunia (difficult or painful sexual intercourse), dysuria (painful or difficult urination), nocturia (waking at night to urinate), incontinence (the involuntary loss of urine), urine frequency, urine urgency, and UTI.

Primary Objective	Evaluation of the subjective effects of fCO ₂ laser therapy on overall urogenital symptoms.
Secondary Objective	Assess vaginal pH and bacteria, overall vaginal health, urinary symptoms, sexual function, UTI frequency, and mental health status.
Primary Outcome	The mean and median response to treatment as measured by the Patient Global Impression of Improvement (PGI-I) questionnaire
Secondary Outcomes	Change in vaginal pH and overall vaginal health on physical examination as measured by the Vaginal Health Inventory Score (VHIS) Change in urinary symptoms as measured by the Questionnaire for Urinary Incontinence Diagnosis (QUID), OAB symptoms as measured by the Overactive Bladder Questionnaire-Short Form (OAB-q SF), cough stress test and voiding diaries Change in sexual function, including dyspareunia symptoms, as measured by the Female Sexual Function Inventory (FSFI) Change in the frequency of UTI occurrences Change in mental health status as measured by the Generalized Anxiety Disorder Questionnaire (GAD-7) and Patient Health Questionnaire (PHQ-8) Change in life and sexual impact of vulvovaginal skin symptoms as measured by the Incontinence Quality of Life Questionnaire (I-QOL) Change in the presence of lactobacillus, assessed by vaginal swab
Primary Endpoint	Week 16 (4 weeks post-treatment).
Secondary Endpoints	Primary and secondary outcomes will be evaluated again at Visit 4 (6-month follow-up) Primary and secondary outcomes will be evaluated again at Visit 10 (36-month follow-up)

SECTION II: METHODOLOGY

This is a prospective observational study of patients undergoing vaginal treatment with the fCO₂ laser for various urogenital symptoms. We anticipate enrolling approximately 100 women in this study. The majority of patients are expected to be recruited from the WUC and private Urology offices. Informed consent will be obtained before any study activities are conducted. Women who meet all of the eligibility criteria will be enrolled in the study. Three treatments with the fCO₂ laser to the vagina will be performed, approximately six weeks apart. The patient will follow up every three months for the first year, then every six months for the following two years, for a total of three years of follow-up.

At each follow-up visit, the patients will complete specified questionnaires. The patient will be offered a repeat treatment at 1, 2 and 3 years if initial treatment efficacy has decreased. A pelvic examination will be performed at Visits 4 (6-month follow up), 6 (12-month follow up), 8 (24-month follow up), and 10 (36-month follow up) and the clinician will complete a cough stress test and the VHIS, including vaginal pH.

Patients will be advised to refrain from:

- vaginal intercourse for 24 hours prior to all visits.
- starting vaginal or systemic hormone therapy or use of new vaginal lubricants during the first six months of the study.
- starting any other preventative therapies for UTIs including antibiotic suppression, cranberry supplements, or d-mannose during the first six months of the study.
- starting any new treatments (i.e. pharmacologic, physical therapy) for overactive bladder (OAB) or stress urinary incontinence (SUI) during the first six months of the study.

Study patients will not be compensated for their participation in the trial. However, all research related activities, specified on the table of events, will be provided at no cost to the study patient.

Inclusion/Exclusion Criteria

Inclusion criteria:

- Female
- ≥18 years and ≤90 years of age
- One or more of the following indications for fCO₂ laser treatment:
 - Genitourinary symptoms of menopause, including after natural, medically-induced, or surgical menopause
 - Vaginal dryness, burning, itching, or dyspareunia not related to menopause
 - Recurrent UTIs, defined as 4 or more in a year
 - Overactive bladder
- Must sign the informed consent form
- Must be willing to comply with the study protocol

Exclusion criteria:

- Contraindications to fCO₂ laser treatment, such as:
 - currently implanted synthetic pelvic mesh, sling, or tape
 - current or previous genital cancers
 - radiation to the vaginal or colo-rectal tissue
 - currently pregnant or less than 3 months following pregnancy
 - undiagnosed vaginal or cervical lesions

- Patients who have received vaginal fCO₂ laser treatment within the past 12 months
- Patients treated with vaginal estrogen within the past 3 months
- Patients with undiagnosed vaginal bleeding
- Active vulvar or vaginal infection, including herpes, candidiasis, etc.
- Current UTI, confirmed by positive urine culture and patient-reported UTI symptoms
- Pelvic or vaginal surgery within the past 9 months
- Pelvic organ prolapse beyond the introitus
- Patient possesses any other characteristics that, per the investigator's judgment, deems them unsuitable (i.e. may increase patient's risk, may affect the conduct of the study, etc.) for the treatment and/or study
- Participation in an investigational trial that used a study treatment, medication and/or biologic within 6 months or less prior to the date of the screening visit

Deferral

Patients may be deferred and rescreened at a later date under the following conditions:

- Patients with active vulvar or vaginal infections may be rescreened after treatment
- Patients with an active UTI may be rescreened after treatment
- Patients with undiagnosed vaginal bleeding may be rescreened after complete work-up, treatment and resolution of vaginal bleeding
- Patients pregnant within the past 3 months
- Patients who have received vaginal fCO₂ laser treatment within the past 12 months
- Patients treated with vaginal estrogen within the past 3 months
- Patients with recent pelvic or vaginal surgery within the past 9 months

Study Visits

Visit 0 – Baseline

Consent to send out a medical history form may be done by telephone script with all elements of information sheet included. Participant agreement is consent to send the medical history form. Once the participant is present for Visit 0, a formal consent will be performed for study participation. Informed consent will be obtained from all participants prior to conducting any study activities. Screening activities will be conducted to determine eligibility. Information will be provided from available medical records and patient self-report. Medical history, demographics, and current medications will be reviewed and recorded. Urine dipstick will be done to rule out active UTI. If UTI symptoms are reported and urine dipstick is positive for nitrates and/or leukocytes, a urine C&S will be sent to the laboratory. Urine pregnancy test will be done in women of childbearing capability. The patient will complete a three-day voiding within 1 week before Visit 1, which will be collected at Visit 1.

Visit 1 – Treatment 1

Visit 1 will, ideally, take place within 4 weeks of Visit 0. If Visit 1 occurs more than 4 weeks after Visit 0, then staff will review medical history and concomitant medications with the subject to ensure they are still eligible to participate in the study. Urine dipstick, and urine culture will be performed, if indicated. UTI symptoms will be assessed (presence or absence of dysuria, foul change in urine odor, change in sediment, urgency, incontinence episodes). If a UTI is suspected, treatment will be deferred until the UTI is diagnosed and, if required, treated. Urine pregnancy test will be done in women of childbearing capability. Patient will complete the Vulvovaginal Symptom Questionnaire (VSQ), Incontinence Quality of Life (I-QOL) questionnaire, Questionnaire for female Urinary Incontinence Diagnosis (QUID), OAB-q SF, FSFI, GAD-7, and PHQ-8 prior to treatment. A vaginal exam, including a cough stress

test and VHIS, will be performed. A vaginal swab will be collected for wet mount and examined microscopically for presence of lactobacillus. The fCO₂ laser treatment will be performed, and the patient will score discomfort using the VAS. The provider will score the difficulty of administering the treatment using the VAS. Adverse events (AEs) will be assessed throughout the visit. The patient will complete a three-day voiding diary within 1 week prior to Visit 2, which will be collected at Visit 2.

Visit 2 – Treatment 2 (6 weeks +/- 2 weeks after Visit 1)

Current medications and AEs will be assessed. Urine dipstick, and urine culture will be performed, if indicated. UTI symptoms will be assessed. Urine pregnancy test will be done in women of childbearing capability. The patient will complete a PGI-I for symptom improvement, VSQ, I-QOL, QUID, OAB-q SF, FSFI, GAD-7 and PHQ-8. A vaginal exam, including a cough stress test and VHIS, will be performed. A vaginal swab will be collected for wet mount and examined microscopically for presence of lactobacillus. The fCO₂ laser treatment will be performed, and patient will score discomfort using the VAS. The provider will score the difficulty of administering the treatment using the VAS. The patient will complete a three-day voiding diary within 1 week prior to Visit 3, which will be collected at Visit 3.

Visit 3 – Treatment 3 (6 weeks +/- 2 weeks after Visit 2)

Current medications and AEs will be assessed. Urine dipstick, and urine culture will be performed, if indicated. UTI symptoms will be assessed. Urine pregnancy test will be done in women of childbearing capability. The patient will complete a PGI-I for symptom improvement, VSQ, I-QOL, QUID, OAB-q SF, FSFI, GAD-7 and PHQ-8. A vaginal exam, including a cough stress test and VHIS, will be performed. A vaginal swab will be collected for wet mount and examined microscopically for presence of lactobacillus. The fCO₂ laser treatment will be performed, and patient will score discomfort using the VAS. The provider will score the difficulty of administering the treatment using the VAS. The patient will complete a three-day voiding diary within 1 week prior to Visit 4, which will be collected at Visit 4.

In the event that scheduling difficulties result in treatment visits out of window, the treatment visits will take place no less than 4 weeks apart.

Phone Call (4 weeks +/- 1 week after Visit 3)

Research staff will contact the patient by phone to assess for AEs and administer the PGI-I for overall urogenital symptoms and Perception of Monetary Value.

Visit 4 - 6 Month Follow up (3 months +/- 2 weeks after Visit 3)

Current medications and AEs will be assessed. Urine dipstick, and urine culture will be performed, if indicated. UTI symptoms will be assessed. The patient will complete a PGI-I for symptom improvement, VSQ, I-QOL, QUID, OAB-q SF, FSFI, GAD-7 and PHQ-8. A vaginal exam, including a cough stress test and VHIS, will be performed. A vaginal swab will be collected for wet mount and examined microscopically for presence of lactobacillus.

Visit 5 – 9 Month Follow up (3 months +/- 2 weeks after Visit 4)

Current medications and AEs will be assessed. Urine dipstick, and urine culture will be performed, if indicated. UTI symptoms will be assessed. The patient will complete a PGI-I for symptom improvement, VSQ, I-QOL, QUID, OAB-q SF, FSFI, GAD-7 and PHQ-8. The patient will complete a three-day voiding diary within 1 week prior to Visit 6, which will be collected at Visit 6.

Visit 6 – 1 Year Follow up (3 months +/- 2 weeks after Visit 5)

Current medications and AEs will be assessed. Urine dipstick, and urine culture will be performed, if indicated. UTI symptoms will be assessed. Urine pregnancy test will be done in women of childbearing capability. The patient will complete a PGI-I for symptom improvement, VSQ, I-QOL, QUID, OAB-q SF, FSFI, GAD-7, PHQ-8, and Perception of Monetary Value. A vaginal exam, including a cough stress test and VHIS, will be performed. A vaginal swab will be collected for wet mount and examined microscopically for presence of lactobacillus. If the patient feels her symptoms have returned and she requests a repeat treatment this will be discussed with the investigator. If the investigator determines, in his/her clinical judgment, a treatment is appropriate the fCO₂ laser treatment will be performed. The patient will score discomfort using the VAS. The provider will score the difficulty of administering the treatment using the VAS.

Visit 7 – 18 Month Follow up(6 months +/- 2 weeks after Visit 6)

Current medications and AEs will be assessed. Urine dipstick, and urine culture will be performed, if indicated. UTI symptoms will be assessed. The patient will complete a PGI-I for symptom improvement, VSQ, I-QOL, QUID, OAB-q SF, FSFI, GAD-7 and PHQ-8. The patient will complete a three-day voiding diary within 1 week prior to Visit 8, which will be collected at Visit 8.

Visit 8 – 2 Year Follow up (6 months +/- 2 weeks after Visit 7)

Current medications and AEs will be assessed. Urine dipstick, and urine culture will be performed, if indicated. UTI symptoms will be assessed. Urine pregnancy test will be done in women of childbearing capability. The patient will complete a PGI-I for symptom improvement, VSQ, I-QOL, QUID, OAB-q SF, FSFI, GAD-7 and PHQ-8. A vaginal exam, including a cough stress test and VHIS, will be performed. A vaginal swab will be collected for wet mount and examined microscopically for presence of lactobacillus. If the patient feels her symptoms have returned and she requests a repeat treatment this will be discussed with the investigator. If the investigator determines, in his/her clinical judgment, a treatment is appropriate the fCO₂ laser treatment will be performed. The patient will score discomfort using the VAS. The provider will score the difficulty of administering the treatment using the VAS.

Visit 9 – 30 Month Follow up (6 months +/- 2 weeks after Visit 8)

Current medications and AEs will be assessed. Urine dipstick, and urine culture will be performed, if indicated. UTI symptoms will be assessed. The patient will complete a PGI-I for symptom improvement, VSQ, I-QOL, QUID, OAB-q SF, FSFI, GAD-7 and PHQ-8. The patient will complete a three-day voiding diary within 1 week prior to Visit 10, which will be collected at Visit 10.

Visit 10 – 3 Year Follow up (6 months +/- 2 weeks after Visit 9)

Current medications and AEs will be assessed. Urine dipstick, and urine culture will be performed, if indicated. UTI symptoms will be assessed. Urine pregnancy test will be done in women of childbearing capability. The patient will complete a PGI-I for symptom improvement, VSQ, I-QOL, QUID, OAB-q SF, FSFI, GAD-7 and PHQ-8. A vaginal exam, including a cough stress test and VHIS, will be performed. A vaginal swab will be collected for wet mount and examined microscopically for presence of lactobacillus. If the patient feels her symptoms have returned and she requests a repeat treatment this will be discussed with the investigator. If the investigator determines, in his/her clinical judgment, a treatment is appropriate the fCO₂ laser treatment will be performed. The patient will score discomfort using the VAS. The provider will score the difficulty of administering the treatment using the VAS.

VAS. If a treatment is given, the participant will be instructed to follow up with the practitioner per standard of care. Visit 10 will be the final visit.

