Laser treatment will be performed as per routine protocol. This includes intra-vaginal treatment based on atrophy level as based on VHIS score and treatment number.

Treatment	Atrophy	Treatment 1	Treatment 2	Treatment 3
Intravaginal	Severe (VHIS 6-15)	Energy: 7.5-10 mJ Density: 10%	Energy: 10 mJ Density: 10%	Energy: 10 mJ Density: 10%
	Moderate (VHIS 16-20)	Energy: 10 mJ Density: 10%	Energy: 10-12.5 mJ Density: 10-15%	Energy: 10-12.5 mJ Density: 10-15%
	Non-atrophic (VHIS >20)	Energy: 10 mJ Density: 10%	Energy: 12.5 mJ Density: 10-15%	Energy: 12.5 mJ Density: 15%

Laser is delivered at 6 points at each level of the vaginal wall: 12, 2, 4, 6, 8, and 10, o'clock of Hart's line. Delivery begins at the most proximal and the wand is retracted by 1 cm and another row of laser treatment is delivered. Number of levels is determined by patient vaginal length.

MEASURES

Cough Stress Test

During a vaginal exam, while the patient is in lithotomy or frog-legged position, the provider will ask the patient to cough and will look for visual signs of a urine leak. Any urine loss observed is indicative of a positive cough stress test.

Female Sexual Function Index (FSFI)

This validated questionnaire is a brief multidimensional scale for assessing sexual function in women. The scale has received initial psychometric evaluation, including studies of reliability, convergent validity, and discriminant validity²⁴.

Generalized Anxiety Disorder 7-item (GAD-7)

This validated questionnaire is used for screening for anxiety with good reliability with sensitivity of 89% and specificity of 82%, for use in clinical practice and in research²⁵.

Incontinence-Quality of Life (I-QOL)

This validated questionnaire is a commonly used self-report quality of life measure specific to urinary incontinence. This tool can be used to assess the impact of urinary problems and their treatment. The I-QOL has 22 questions with the following 3 subscales: avoid and limiting behaviors (items), psychosocial impacts (9 items), and social embarrassment (5 items). It is easily self-administered and takes about 5 minutes to complete.²³

Overactive Bladder Questionnaire-Short Form (OAB-q SF)

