Providers will record the difficulty of performing the treatment on a Visual Analog Scale from 0 (not at all difficult) to 10 (most difficult imaginable).

3-Day Voiding Diary

Patients will record each void and urine leak over a 3 day period. Patients will determine if each leak is a stress leak or an urge leak. They will score the level of urgency they experience with each void, based on the Indevus Urgency Severity Scale (IUSS).

Vulvovaginal Symptom Questionnaire (VSQ)

The VSQ was developed to determine the symptoms, emotions, life impact, and sexual impact of vulvovaginal symptoms on postmenopausal women. The questionnaire is comprised of twenty-one questions with "yes" or "no" responses.

SECTION III: POSSIBLE RISKS AND BENEFITS

Ethical Principles

This project will be approved by William Beaumont Hospital's Institutional Review Board (IRB). Adult patients will provide informed consent prior to any study activity. This study will be conducted pursuant to the Declaration of Helsinki: Recommendation Guiding the Medical Doctors in Biochemical Research Involving Human Subjects. Investigators will follow this clinical investigation plan at all times and follow requirements set by Federal Law and Institutional Review Board regulations at all times.

Risks of Study Procedures

Fractional Carbon Dioxide Laser Treatment

Risks of fractional carbon dioxide laser treatment to the vagina are minimal with no previous adverse events reported. Theoretically, risks may include vaginal irritation, bleeding, infection, and damage to surrounding tissue or structures. There also may be a burning sensation and itching, both mild in nature and resolving within 1-2 days.

Risk of Breach of Privacy and Confidentiality

There is a rare risk of breach of privacy and data confidentiality (release of information which personally identifies the patient). Confidentiality procedures will be strictly adhered to when transferring, managing, and analyzing study data. The patient will be assigned a unique study identification number and research information will be stored in a locked, secure cabinet in the Urology Research suite with access limited to authorized research personnel. Study data will be maintained in a password protected file on a shared network that can only be accessed by Urology research personnel.

Benefits

Patients may experience an improvement in urogenital symptoms. They will receive close clinical follow-up and monitoring throughout the study period.

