A database will be created utilizing RedCap, MS Excel, or equivalent software. Only designated study personnel will have access to the database, which will be stored on the Urology Research Department's shared drive. Access to the computerized system will be password protected. To ensure accuracy of data entry, database entries will be cross-checked against source

documents. The shared drive is backed up nightly to ensure minimal data loss, even in the most catastrophic system failure. The database will be active until all study visits are completed, final monitoring activities have been conducted, and all data queries have been resolved. After that time, the database will be locked, prohibiting any changes to the data.

All study records, including both paper and electronic, will be stored in accordance with all federal and institutional requirements, including, but not limited to, the HIPAA Privacy Rule, the Food and Drug Act, and Medicare policy. The stored data will be kept in a secure, protected manner. All records will be retained, at a minimum, for eleven years beyond study completion.

SECTION V: STATISTICAL CONSIDERATIONS AND DATA ANALYSIS

This is a novel observational study without a comparison group. Therefore, a power calculation is not necessary. Descriptive statistics will be given for all data collected. Patients will be analyzed and described overall as a group, and subgroup analyses will be performed by presenting complaint(s). Missing data will be considered missing and no interpolations or substitutions will be performed. Categorical characteristics will be summarized using frequencies and percentages. Continuous characteristics will be summarized using mean and standard deviation for normally distributed variables and median and 25th and 75th percentiles for those not normally distributed. The changes in the continuous measures from baseline (prior to device implant) to Visit 4 may be examined using paired t tests. We will explore relationships within this group of patients with possible complications using appropriate methods. SAS for Windows version 9.3 Cary, NC or equivalent will be used for all analyses.

SECTION VI: REFERENCES

1. Nappi RE and Kokot-Kierepa M. Women's voices in the menopause: results from an international survey on vaginal atrophy. *Maturitas*. 2010; 67: 233-8.
2. Nappi RE and Palacios S. Impact of vulvovaginal atrophy on sexual health and quality of life at postmenopause. *Climacteric*. 2014; 17: 3-9.

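### The secondary outcome on the impact of vulvovaginal symptoms is measured with an incontinence questionnaire (I-QOL), while the VSQ, which fits it, is named in no outcome

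*Combined protocol and SAP*

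**What the plan says.** The outcome table under Objectives and Outcomes includes this secondary outcome: "Change in life and sexual impact of vulvovaginal skin symptoms as measured by the Incontinence Quality of Life Questionnaire (I-QOL".

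The Measures section describes the two relevant instruments as follows.

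- I-QOL: "This validated questionnaire is a commonly used self-report quality of life measure specific to urinary incontinence". Its three subscales cover avoidance and limiting behaviour, psychosocial impact and social embarrassment.
- VSQ: "The VSQ was developed to determine the symptoms, emotions, life impact, and sexual impact of vulvovaginal symptoms on postmenopausal women". Its format is 21 items answered yes or no. No scoring rule is given.

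Both questionnaires are completed before treatment at Visit 1 and again at every visit from 2 to 10. The Visit 4 text is typical: "The patient will complete a PGI-I for symptom improvement, VSQ, I-QOL, QUID, OAB-q SF, FSFI, GAD-7 and PHQ-8". At the phone call four weeks after Visit 3, which is the primary endpoint, the visit text has staff assess adverse events and "administer the PGI-I for overall urogenital symptoms and Perception of Monetary Value". It mentions neither the VSQ nor the I-QOL.

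Section V names no questionnaire. It states that "Descriptive statistics will be given for all data collected" and allows paired t tests of change from baseline to Visit 4 for continuous measures.

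**The concern.** The outcome names one construct and an instrument for another. Taken literally, the result reported as vulvovaginal impact would be a score for the burden of urine leakage. This could mislead in two ways:

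- A change in leakage could be presented as a vulvovaginal benefit.
- The inclusion criteria admit women on vaginal dryness, burning, itching or dyspareunia alone, with no incontinence required. In such a woman an incontinence scale may move little even if her symptoms improve.

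The outcome list would also have no condition-specific patient-reported vulvovaginal measure beyond sexual function and dyspareunia on the FSFI. The VHIS is scored by the clinician. The PGI-I is a single global rating, so in a woman with both vulvovaginal and urinary complaints it cannot show which of them improved.

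The reverse gap exists too. The vulvovaginal outcome is the only one that names the I-QOL, so incontinence-specific quality of life has no outcome of its own.

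**Working it through.** The plan gives no figure to reproduce here. The check sets the visit text, the outcome table and the Measures section side by side. The Schedule of Activities table is too damaged in the available text to rely on and was not used.

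**Step 1. Questionnaires given at every visit from 2 to 10, against the outcomes that name them**

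| Questionnaire | Outcome that names it |
|---|---|
| PGI-I | Primary |
| QUID | Urinary symptoms |
| OAB-q SF | Urinary symptoms (overactive bladder) |
| FSFI | Sexual function |
| GAD-7 | Mental health |
| PHQ-8 | Mental health |
| I-QOL | Vulvovaginal impact |
| VSQ | None |

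Seven of eight are named. The VSQ is the exception.

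**Step 2. Construct against instrument**

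| Source | Life impact | Sexual impact | Vulvovaginal symptoms | Urinary incontinence |
|---|---|---|---|---|
| Outcome as worded | yes | yes | yes | no |
| VSQ, as described in Measures | yes | yes | yes | no |
| I-QOL, as described in Measures | yes (quality of life) | not described | not described | yes |

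The VSQ description matches all three elements of the outcome. The I-QOL description shares only the general idea of effect on life, and ties it to incontinence.

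**Step 3. Share of the outcome list affected.** The secondary outcomes are (1) VHIS and vaginal pH, (2) urinary symptoms, (3) sexual function, (4) UTI frequency, (5) mental health, (6) vulvovaginal impact and (7) lactobacillus. One of the seven is affected.

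**Step 4. Amount of VSQ data without a named role.** The inputs are about 100 women and 10 visits (Visits 1 to 10).

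- Ceiling with full attendance: 10 × 100 = 1,000 forms.
- The protocol gives no attrition rate. Assume full completion at Visits 1 to 3 and 60% to 80% at the seven visits from 4 to 10:
  - at 80%: 3 × 100 + 7 × 80 = 860
  - at 60%: 3 × 100 + 7 × 60 = 720

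These counts describe the volume of data, not the harm. The conclusion does not depend on them.

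**Step 5. Search for a repair elsewhere.** Section V does not mention the VSQ, and no other section links it to an outcome. The promise of descriptive statistics for all data means the VSQ would be tabulated, but not as the named outcome.

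**The case against.** The strongest reply is that little hangs on this outcome. The study has no comparison group and no power calculation, no test or decision rule is tied to this outcome, and paired t tests are only optional. The VSQ will be collected and summarised in any case. The primary PGI-I covers overall urogenital symptoms, which the protocol defines to include vaginal itching, burning and dryness, and Section V promises subgroup analyses by presenting complaint. A reader who sees the I-QOL's full name may also notice that it concerns incontinence. All of this stands, and it limits the consequence. It does not make the I-QOL a measure of vulvovaginal impact.

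Second, the VSQ is not the only item collected without a named outcome. Perception of Monetary Value and the two visual analogue scales are not named either. That is correct, but the first is given only at the 16-week call and the 12-month visit, and the scales belong to treatment sessions. The count of seven in eight concerns the set repeated at every visit from 2 to 10, and for that set it is exact.

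Third, the authors' intent is not stated. One instrument may have replaced another, or two outcomes (VSQ for vulvovaginal impact, I-QOL for incontinence quality of life) may have been merged. This affects where the I-QOL should go, but under either reading the VSQ belongs to the vulvovaginal outcome.

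Fourth, the VSQ is described for postmenopausal women, while eligibility is wider. This is a real limit on the VSQ, but no argument for an incontinence scale.

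Finally, the absence of secondary questionnaires from the week 16 call is not peculiar to this outcome. That is also true, and the authors may wish to settle the time points for all secondary outcomes together.

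**Conclusion.** The concern holds and should be fixed. One of seven secondary outcomes names an instrument that the protocol itself describes as measuring something else. The matching instrument, already collected at ten visits, has no outcome. This is an error in the text as written, not merely a missing detail. If the analysts quietly used the VSQ later, they would be making an undocumented change of outcome measure.

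The consequence is limited: the primary outcome is untouched and no data are lost. The documents give no case mix, so the share of women with vulvovaginal complaints cannot be stated. The conclusion rests only on the protocol's own descriptions of the two questionnaires.

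**What to change.** 1. In the secondary outcomes, name the VSQ as the measure of life and sexual impact of vulvovaginal symptoms.
2. Move the I-QOL to the urinary-symptom outcome beside the QUID and OAB-q SF. If the authors intended two outcomes, give the I-QOL a separate incontinence quality-of-life outcome instead.
3. State the VSQ score. The instrument's own scoring rule is preferable. Failing that, use the number of yes answers (0 to 21), show the life-impact and sexual-impact items separately, and list which items those are.
4. State the comparisons as Visit 1 to Visit 4 and Visit 1 to Visit 10. These match the secondary endpoints, and the text for the week 16 call includes neither questionnaire.
5. Optionally, show the VSQ descriptively by menopausal status.

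The cost is an edit to two outcome lines and one or two added sentences. There is no new data collection and no added burden on patients, because both questionnaires are already completed at Visits 1 to 10.
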